4.1.3 Phase 1b Pilot of STORM-e (months 5-8)

In phase 1b, the adapted intervention will be piloted with four groups (approximate N = 20), giving priority to groups that already expressed interest in participating in the STORM study. The average anticipated pilot group size of n=5 arises from feedback received during our stakeholder consultations that smaller group sizes work better in web meetings. This group size is also likely to mirror smaller group sizes we would be likely to encounter in any future feasibility study comparing F2F STORM with STORM-e, due to social restrictions that may affect work for some time to come. Of the four pilot groups, at least one will need to do some additional work to allow all its group members to access STORM-e, in order to allow us to explore 'live' how issues around access to technology, support, and provisions to ensure privacy are managed.

Following facilitator training, all STORM-e sessions will be recorded locally in line with data protection regulations. The recordings will be used alongside STORM-e facilitator records and notes kept in supervision to identify what challenges to implementing STORM-e as planned arose and how these were managed. The insights gained will help us identify the need for further revisions to the manual and/or delivery mechanisms ahead of a feasibility study.

To understand implementation of STORM-e, we will monitor what proportion of pilot participants needed help to access the digital intervention and what this help consisted of. For those participants who received support to access STORM-e, we will monitor how participant privacy is assured, whether

Trials Research Canolfan Ymchwil Treialon

threats to privacy arise, what their impact is on participant engagement, and whether following the manual allows STORM-e facilitators to manage these or whether additional guidance is needed. These issues will be assessed via facilitator notes, session recordings and interviews with participants and facilitators.

We will ask group facilitators to record group members' attendance at each session and occasions when group members experienced access and/or internet connection problems. Facilitators will also be asked to note down after each session challenges to delivering the intervention as intended and to participant engagement and to bring these notes for discussion in supervision. Feedback on how they addressed challenges and the impact will be elicited in supervision and shared with the research team. Additionally, we will use the session recordings to triangulate facilitators' records and assess what proportion of the sessions participants were able to attend (to account for participants dropping out at any point, either due to poor internet connection or for other reasons).

At the end of the last STORM-e session of each pilot group, our PPI advisors will act as peer researchers and co-lead a group discussion to obtain participants' views on STORM-e, what went well and what got in the way of their taking part and potentially benefitting from the intervention. They will explore whether ethical risks, including instances where individual participants needed practical or emotional support and risks to privacy during sessions, were managed in an acceptable manner. Postintervention outcome measures will be completed with all pilot participants as soon as is feasible after the last STORM-e session.

A researcher will interview each pilot group facilitator about their experiences of delivering STORMe. Interview data will be combined with supervision notes kept by the Mencap intervention lead to assess barriers and facilitators to STORM-e implementation.

During the pilot we will also test our revised plans for the process evaluation of STORM-e. This will include assessing the feasibility of recording of STORM-e sessions by facilitators locally and sharing of recordings with the research team to ensure compliance with data protection regulations. We will assess whether these recordings can be used to assess adherence and attrition or whether facilitator records need to be combined with review of session recordings to achieve this.

The outputs from Phase 1b will be:

(a) an adapted intervention manual for delivery of STORM-e that can be tested within a feasibility study;

(b) a revised logic model that incorporates what we have learnt during the pilot about mode of delivery and contextual factors;

(c) a description of UP across third sector organisations in the wake of the Covid-19 pandemic;

(d) a revised outcome assessment protocol suitable for virtual delivery for use within a feasibility study, and

(e) data regarding the feasibility of collecting outcome data remotely.

4.1.4 Phase 1c Decision phase

During the adaptation work, the SMG and SSC will meet at regular intervals to monitor progress of the work, focusing on these milestones:

Month 4: Successful recruitment of groups for pilot

Month 5: Completion of manual adaptation

Month 8: Completion of pilot

During month 8, the SMG will meet to review the progress and preliminary findings from the STORMe pilot. In particular, it will consider key indicators of successful adaptation, and also whether the original F2F version of STORM is feasible at that point in time. If both the online and F2F versions of STORM appear feasible, they will consider what questions need to be addressed about the design of a potential future definitive RCT and may recommend seeking funding for a feasibility study. In case STORM-e was shown to be feasible but the original F2F version of STORM was still not feasible, the SMG may conclude that a 2-arm study of STORM-e versus UP is indicated. In case STORM-e emerged as not feasible for some reason during the adaptation work and piloting but the original F2F version was feasible, the original 2-arm study of STORM versus UP could be pursued.

During month 9, the SSC will be convened to consider the outputs and SMG's recommendations. Using the indicators of successful adaptation outlined below they will make a recommendation to the NIHR PHR programme whether a funding application for progression to a feasibility trial is justified, and if so what design and interventions are to be employed.

1. Feasibility of delivery of STOF supervision notes, and review	v of session recordings demonstra	records and feedback, ate:		
Poor indicator for progression	Indicator for progression, with	Strong indicator for		
	further adaptations needed	progression		
 attendance was poor (participants on average attended less than 3 sessions and within session presence and engagement was poor, unlikely to be resolved with adaptations technical problems were significant, were not resolvable and likely to severely impair future implementation would not recommend STORM-e to others nor consider running it with other groups 	 good attendance across sessions (participants on average attended at least 3 sessions), BUT, presence and engagement within sessions was somewhat impaired by technical issues. These would be resolvable with some additional modifications/guidance. would only consider recommending STORM-e to others or running another group if specific changes were made to the 	 good attendance across sessions (participants on average attended at least 3 sessions) and presence and engagement within sessions was good, any technical problems were resolvable and did not unduly impact on running the session or engagement would recommend STORM-e to others and consider running it with another group felt able to monitor 		
	content, structure or	participants' emotional		

..... *.*

 felt unable to monitor participants' emotional responses during sessions and to respond accordingly, modifications unlikely to resolve this. felt modifications were needed to monitor participants' emotional responses during sessions and to respond accordingly felt modifications were needed to monitor participants' emotional responses during sessions and to respond accordingly, barthese significantly impacted on engagement and participation. Further modifications unlikely to adequately resolve this. privacy could be better modifications privacy could be better managed with some modifications 						
managed with some modifications	-	felt unable to monitor participants' emotional responses during sessions and to respond accordingly, modifications unlikely to resolve this. privacy threats were evident and unmanageable or significantly impacted on engagement and participation. Further modifications unlikely to	-	accessibility of the technology. felt modifications were needed to monitor participants' emotional responses during sessions and to respond accordingly, but these would be straightforward to implement through additional guidance or adaptations.	-	responses during sessions and to respond accordingly able to manage any threats to privacy for group members either by following the manual or taking additional steps

acceptable and would not recommend STORM-e to others. Changes unlikely to remedy this.and would recommend STORM-e to others without changes.STORM-e as acceptable and would recommend STORM-e to otherson occasion when participants may have found intervention contents distressing, they either felt un-supported by the group facilitator and/or their peers, or were un-able to access support outside of-on occasion when participants may have found the intervention contents distressing, they did not always feel well supported by the group facilitator and/or their peers, or were un-able to access support outside of-on occasion others on occasion when participants may have found the intervention contents distressing, they either felt supported by the group facilitator and/or their peers, or were un-able to access support outside of-on occasion when participants may have found the intervention contents distressing, they either felt well supported by the group facilitator and/or their peers, or were able to access support outside of the
recommend STORM-e to others. Changes unlikely to remedy this.STORM-e to others without changes.and would recommend STORM-e to others on occasion when participants may have found intervention contents distressing, they either felt un-supported by the group facilitator and/or their peers, or were un-able to access support outside ofSTORM-e to others without changeson occasion when participants may have found the intervention contents distressing, they did not always feel well supported by the group facilitator and/or their peers, or were un-able to access support outside ofSTORM-e to others. on occasion when participants may have found the intervention contents distressing, they either felt well supported by the group facilitator able to access support
others. Changes unlikely to remedy this.without changes.STORM-e to others on occasion when participants may have participants may have found intervention contents distressing, they either felt un-supported by the group facilitator and/or their peers, or were un-able to access support outside of- on occasion when participants may have found the intervention contents distressing, they did not always feel well supported by the group facilitator and/or their peers, or were un-able to access support outside of- on occasion when participants may have found the intervention contents distressing, they did not always feel well supported by the group facilitator and/or their peers, or were not always able to access support- on occasion when participants may have found the intervention contents distressing, they either felt well supported by the group facilitator and/or their peers, or were able to access support outside of the
 remedy this. on occasion when participants may have found intervention contents distressing, they either felt un-supported by the group facilitator and/or their peers, or were un-able to access support outside of on occasion when participants may have found the intervention contents distressing, they did not always feel well supported by the group facilitator and/or their peers, or were un-able to on occasion when participants may have found the intervention contents distressing, they did not always feel well supported by the group facilitator and/or their peers, or were not always able to access support on occasion when participants may have found the intervention contents distressing, they either felt well supported by the group facilitator and/or their peers, or were able to access support outside of the
 on occasion when participants may have found intervention contents distressing, they either felt un-supported by the group facilitator and/or their peers, or were un-able to access support outside of the access support outside of the access support outside of the access support outside of the access ac
participants may have found intervention contentsfound the intervention contents distressing, they did not always feel well supported by the group facilitator and/or their peers, or were un-able to access support outside offound the intervention contents distressing, they did not always feel well supported by the group facilitator and/or their able to access supportfound the intervention contents distressing, they either felt well supported by the group facilitator and/or their support outside of
intervention contentscontents distressing, theycontents distressing, theydistressing, they either feltdid not always feel welleither felt well supportedun-supported by the groupsupported by the groupby the group facilitatorfacilitator and/or theirfacilitator and/or theirand/or theirpeers, or were un-able topeers, or were not alwayswere able to accessaccess support outside ofable to access supportsupport outside of the
distressing, they either feltdid not always feel welleither felt well supportedun-supported by the groupsupported by the groupby the group facilitatorfacilitator and/or theirfacilitator and/or theirand/or theirpeers, or were un-able topeers, or were not alwayswere able to accessaccess support outside ofable to access supportsupport outside of the
un-supported by the group facilitator and/or their peers, or were un-able to access support outside ofsupported by the group facilitator and/or their peers, or were not always able to access supportby the group facilitator and/or their peers, or were able to access support outside of the
facilitator and/or their peers, or were un-able to access support outside offacilitator and/or their peers, or were not always able to access supportand/or their peers, or were able to access support outside of the
peers, or were un-able to access support outside of thepeers, or were not always able to access support outside of thewere able to access support outside of the
access support outside of able to access support support outside of the
the group. Changes unlikely outside of the group when group
to remedy this. they needed it. Changes - participant privacy was
- participant privacy was not would mean that support maintained in a way that
maintained in a way that in this area could be allowed full engagement
allowed them to fully improved. in the sessions.
engage in the sessions participant privacy was
Changes unlikely to remedy mostly maintained but
this. there were occasions
when threats to privacy
affected engagement
and/or raised concern.
Changes in this area could

≜UCL

make this more	
acceptable in the future.	

The risk of exclusion from STORM-e due to technical issues will be considered in relation to a target of no participant missing more than two sessions, or parts thereof (other than brief connectivity problems not exceeding 10 to 15 minutes), due to technical problems.

A decision whether it is feasible to collect outcome data remotely will be informed by responses to collection of baseline data during the pilot. Should 80%+ of collected outcome data be usable this will be deemed feasible, if 70%-79% of collected outcome data are usable we will review and revise the procedures for remote data collection. If less than 70% of collected outcome data are usable, we will consider with the SMG and SSC whether there are strategies to improve this (e.g., drawing on data from our UKRI/NIHR Covid-19 study with people with ID) or whether remote collection of data is not feasible.

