Exclusion criteria	 Groups will be excluded if: they are run as part of NHS services; some of their regular members decline taking part in STORM-e and it is not possible to find alternative meeting times to run STORM-e. Participants will be excluded from the research if they do not meet any of the inclusion criteria or do not provide consent. 		
Intervention	STORM-e: web delivered adaptation of STORM, consisting of 4 weekly 90- minute sessions and a 90-minute follow-up session (delivered around four weeks after session 4).		
Primary objective of adaptation phase	To carefully adapt the STORM intervention to a web delivered version and pilot this to assess whether it is practical to deliver this version to established groups of people with ID in a range of community, social and educational settings. The findings will be used to inform the decision whether a subsequent feasibility trial is indicated (which may be a 3-arm trial of both versions of STORM, a 2 arm trial of one STORM version, or potentially no trial).		

Secondary objectives of adaptation phase	To assess the feasibility of collecting all planned outcome data digitally. To characterise 'Usual Practice' in a changed service delivery context.
Primary outcomes of adaptation phase	Adaptation phase: Acceptability of delivering STORM to groups in web delivered format
Secondary outcomes of adaptation phase	Adaptation phase: Feasibility of remotely collecting outcome and process data. Description of 'Usual practice' in a changed service delivery context.
Planned study period	Revised design to include 8 months for adaptation to STORM-e and piloting. 3 months for analysis and reporting.

2 Revised study summary & schema

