4.1.2 Other activities during months 1-4

Concurrently with adaptation of the manual, during months 1-4 the research team will also:

- (a) seek to characterise Usual Practice (UP). This will be achieved through an online survey of existing third sector organisations across the UK. Our survey will include questions about what discussion/conversation based group meetings are delivered, by whom, mode of delivery, location, and where UP has been modified in response to Covid-19, what changes have been made and how well they have worked. This survey will be delivered using Qualtrics and disseminated via our existing contacts, social media channels, and our partner organisations Mencap, the Foundation for People with Learning Disabilities and People First Dorset. We will also complete desk research on published and grey literature on virtual group support for people with ID during the current pandemic.
- (b) test digital delivery of the outcome measures at baseline. All procedures for supporting remote administration of study measures will be finalised as part of this adaptation phase. We will also draw on the experience of the first wave of data collection in a current UKRI/NIHR funded Covid-19 study of people with ID (research team members [name], [name] and [name] are project members). Any queries or difficulties will be resolved in collaboration with the self-advocate PPI advisers who have already provided input on the plans for outcome measurement during the earlier stages of this project. Digital administration of the outcome measures to all STORM-e pilot participants, along with evidence from parallel research studies, will inform the team whether it is feasible to collect outcome data for a feasibility trial using digital methods. If successful, this will mean we can re-consider our sampling procedures and expand the geographical regions we can recruit from for the feasibility trial.

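### The remote-collection feasibility bands name only baseline and count only collected data, so they cannot detect outcome measures that are not completed after the intervention

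*Combined protocol and SAP*

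**What the plan says.** The decision rule is in section 4.1.4 (Phase 1c Decision phase): "A decision whether it is feasible to collect outcome data remotely will be informed by responses to collection of baseline data during the pilot". Three bands follow:

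- Top band: "Should 80%+ of collected outcome data be usable this will be deemed feasible".
- Middle band, from 70% to 79% usable: the collection procedures are to be reworked.
- Lowest band, under 70% usable: the two oversight committees discuss with the team if remote collection can be improved or must be judged not feasible.

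All three percentages refer to data that were collected. Section 4.1.2(b) describes the corresponding activity as a plan to "test digital delivery of the outcome measures at baseline". It adds, without giving a time point, that "Digital administration of the outcome measures to all STORM-e pilot participants, along with evidence from parallel research studies, will inform the team"; the question there is the feasibility of digital collection in a later trial.

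Section 4.1.3 plans a second collection: "Postintervention outcome measures will be completed with all pilot participants as soon as is feasible after the last STORM-e session". No section attaches a threshold to it.

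The Synopsis lists "Feasibility of remotely collecting outcome and process data" as a secondary outcome. The matching secondary objective extends to all the outcome data planned and is not limited to baseline.

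**The concern.** A later trial would estimate its effect from outcomes measured after the intervention. Participants who complete baseline and then miss the later assessment leave no trace in baseline data. A rule that names baseline alone can therefore return feasible whatever happens at follow-up.

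The denominator adds a second difficulty. A measure that was never completed was never collected, so it drops out of a percentage taken over collected data. Applying the bands to the post-intervention data as they stand would still not expose non-completion.

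The result contributes to the Study Steering Committee's recommendation on whether to seek funding for a feasibility trial and with what design. Under section 4.1.2(b) it also bears on whether recruitment can extend to more regions.

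**Working it through.** **Inputs from the documents.** Four groups with an average of 5 members (section 4.1.3) give N = 4 × 5 = 20, which reproduces the stated sample size. The bands are 80% or more, 70% to 79%, and below 70% (section 4.1.4). At N = 20, 80% is 16 and 70% is 14. The Synopsis gives four weekly sessions and a follow-up session about four weeks after session 4. If that follow-up is the last session, post-intervention measures fall about 3 + 4 = 7 weeks after session 1.

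**Assumptions.** The documents give no usability or attrition rate. I take one set of measures per participant as the unit, 90% of returned sets usable at both time points, and retention r varied from 100% to 60%.

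**Expected readings at r = 80%.**

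- Baseline: 0.90 × 20 = 18, and 18/20 = 90%, feasible.
- Post-intervention sets returned: 0.80 × 20 = 16. Usable: 0.90 × 16 = 14.4.
- Usable out of collected: 14.4/16 = 90%, feasible.
- Usable out of expected: 14.4/20 = 72%, review and revise.
- Both time points pooled over expected data: (90% + 72%)/2 = 81%, feasible. Pooling would hide the loss, so the time points need separate figures.

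**Chance of each result.** Let X be the number of usable sets among 20 expected, binomial with p = 0.90 × r. At baseline p = 0.90, and P(X ≥ 16) = 0.957 whatever the later retention. For post-intervention data with all 20 as denominator:

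| Retention r | p | P(X ≥ 16), feasible | P(X < 14), lowest band |
|---|---|---|---|
| 100% | 0.90 | 0.957 | 0.002 |
| 90% | 0.81 | 0.673 | 0.069 |
| 80% | 0.72 | 0.302 | 0.317 |
| 70% | 0.63 | 0.086 | 0.655 |
| 60% | 0.54 | 0.015 | 0.888 |

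**Precision.** The exact 95% interval is 56.3% to 94.3% for 16/20 and 45.7% to 88.1% for 14/20. These treat participants as independent.

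**Is non-completion covered elsewhere?** Section 4.1.4 has an attendance indicator (an average of at least 3 sessions) and a target on sessions missed for technical reasons. Section 4.1.3 plans to assess attrition from recordings and facilitator records. All of these concern sessions; none sets a criterion for completing the outcome measures.

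**The case against.** The strongest reply is that the plan does not confine the decision to baseline. It says the decision is informed by baseline collection. Section 4.1.2(b) brings in administration to all pilot participants and parallel studies, with no time point. Section 4.1.3 lists data on remote collection among the Phase 1b outputs, which the Study Steering Committee will consider. A reader might infer that post-intervention data have no role at all; the documents do not support that. What stands is narrower: baseline is the only pilot time point named for the numerical bands.

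A reader might also infer that the plan has no retention measure. It has session attendance and attrition measures. What is missing is a criterion for completion of outcome measures at follow-up.

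A third tempting inference is that 12 usable sets from 20 participants would fall below 70% under the present bands. If the other 8 were never collected, the stated metric is 12/12 = 100%, not 12/20 = 60%. This is why the denominator has to change as well as the time point.

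Nor do the documents show that baseline is the more favourable occasion in every respect. Drop-out can only lower later completion, but usability among those who respond could improve as participants become used to meeting online.

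Finally, this is a secondary outcome in a pilot of about 20 people, and a proportion near 80% is too imprecise to separate the bands well. That limits the severity. It applies equally to the baseline figure, so it is no reason to leave follow-up out.

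**Conclusion.** The point holds in this form: as worded, the bands cannot detect non-completion of outcome measures after the intervention, because they name baseline alone and count only collected data. This falls short of the secondary objective and is more than missing detail, since following the rule as written can give a feasible result regardless of follow-up.

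The size depends on retention, which is unknown. Under the assumed 90% usability and 80% retention, the expected readings are 90% at baseline and 72% of expected data after the intervention, one band lower. The chance of reaching 16/20 is 0.957 at baseline and 0.302 after the intervention. With full retention and equal usability the two agree.

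I would rate it as a moderate correction worth making before pilot results are seen, and not as a defect that should stop the pilot.

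**What to change.** Make three changes to the paragraph in section 4.1.4, and align section 4.1.2(b) with them:

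1. State that the decision is informed by collection of both baseline and post-intervention data during the pilot.
2. Define the percentage as usable outcome data divided by all outcome data expected from consented participants, so that a measure not completed counts as not usable. State the unit (item, measure or full set). This is a change of rule and should be described as one.
3. Report the percentage against the existing 80% and 70% bands separately at each time point, and require the post-intervention figure also to reach 80% before collection is called feasible. Other ways of combining the two are defensible, provided the choice is written down in advance.

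The cost is a few sentences and no new data, as both collections are already planned. The rule becomes slightly stricter, and the decision must wait for the last group's post-intervention measures. The schedule does not clearly rule this out: pilot completion and the Study Management Group review both fall in month 8, and the Study Steering Committee meets in month 9. Late measures might reach only the second meeting.

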≜UCL

THE STANDING UP FOR MYSELF (STORM) PSYCHOSOCIAL GROUP INTERVENTION FOR YOUNG PEOPLE AND ADULTS WITH INTELLECTUAL DISABILITIES: ADAPTATION FOR DIGITAL DELIVERY AND PILOT

Sponsor:	University College London (UCL)
Funder:	Public Health Research (PHR), National Institute for Health Research (NIHR)
Funder ref:	17/149/03
REC ref:	UCL Research Ethics 0241/005
ISRCTN ref:	16056848
Internal reference	0241/005
Chief Investigator	[name], Division of Psychology and Language Sciences, UCL

This study is funded by the National Institute for Health Research (NIHR) Public Health Research programme (NIHR PHR Project 17/149/03). The views expressed are those of the author(s) and not necessarily those of the NIHR or the Department of Health and Social Care.

FUNDED BY

NIHR | National Institute for Health Research

1 Synopsis of proposed amendment to study design for adaptation and pilot phase

Development phase	Adaptation of the STORM intervention for digital delivery and piloting		
Study participants	Young people and adults with mild to moderate intellectual disabilities		
Planned sample size	4 groups (approx. N=20) to pilot adapted remote delivered version.		
Inclusion criteria	 Groups that wish to take part in the study will: Be in place already (although group meetings may have been disrupted due to Covid-19 and associated social restrictions); Intend to continue or restart meeting as a group for at least 3 further months; Have at least 3 and no more than 8 members with ID who wish to participate in the intervention; Be willing to replace 5 of their usual meetings with STORM; Have a group facilitator willing to receive training and facilitate the STORM intervention and protocol in either face-to-face or digital form; Organisational support to deliver the study intervention. Individual participants will be: aged 16+ years; have an ID as defined by an administrative definition; albe to complete the outcome measures (with or without support) and engage with the STORM intervention; have access to the internet and a device that can access web meetings, be this via Zoom, Skype, Microsoft Teams or Google Meet; where needed, have support to access web based meetings; have capacity to provide informed consent to participation in the study. 		

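### The remote-data rule in section 4.1.4 is a percentage of collected data, so participants or measures that yield no data cannot lower the score

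*Combined protocol and SAP*

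**What the plan says.** The decision on remote collection is in section 4.1.4 (Phase 1c Decision phase), after the two indicator tables. It "will be informed by responses to collection of baseline data during the pilot". Three bands follow:

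- Top: "Should 80%+ of collected outcome data be usable this will be deemed feasible".
- Middle: "if 70%-79% of collected outcome data are usable we will review and revise the procedures for remote data collection".
- Bottom: "If less than 70% of collected outcome data are usable, we will consider with the SMG and SSC" whether the position can be improved or remote collection is not feasible.

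The denominator is the same in all three. Usable is not defined. No section sets a minimum completion rate for the outcome measures or says that data not obtained count as unusable.

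Elsewhere the intended coverage is complete. The secondary objective in the synopsis (section 1) concerns digital collection of every planned outcome. Section 4.1.2(b) has the measures administered digitally to every pilot participant, and section 4.1.3 plans post-intervention measures for every participant too.

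**The concern.** Remote collection can fail in two ways: the data come back unfit for analysis, or they do not come back. A ratio of usable to collected data sees only the first. Someone who cannot be reached, declines or cannot connect adds nothing to either part of the ratio, and neither does a measure that is never started.

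This is the only numerical criterion in the plan for whether outcome data can be gathered remotely. The steering committee is to use the section 4.1.4 indicators when it advises the funder on a feasibility trial. Section 4.1.2(b) adds that success would let the team reconsider sampling and recruit from a wider area. A pass that ignores absent data could carry into the design of the next study. The rest of section 4.1.4 does count absence: attendance is averaged over participants, and the technical-exclusion target concerns sessions missed. Those criteria relate to intervention sessions and do not cover outcome data.

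**Working it through.** **Inputs.** Section 4.1.3 plans four pilot groups and gives "The average anticipated pilot group size of n=5". The cut-offs of 80% and 70% are from section 4.1.4. They are chosen thresholds with no derivation to reproduce.

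**Plan's own figure.** 4 groups × 5 = 20, which matches the stated approximate sample size.

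**Assumptions.** The documents give no completion rate, so a range is shown. For simplicity each participant counts as one unit of data.

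**Formulas.** Let E be the units expected, C the units collected and U the units usable.

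- Rule as written: R = U / C.
- Quantity that the objective needs: P = U / E = (C / E) × (U / C).

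Since C cannot exceed E, P cannot exceed R. The two agree only when everything expected is collected, or when nothing is usable.

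**Cut-offs on E = 20.** 0.80 × 20 = 16 participants with usable data; 0.70 × 20 = 14.

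**Case 1: everything returned is usable (U = C).**

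| Return data | R = U/C | P = U/20 | Band under P |
|---|---|---|---|
| 18 | 100% | 90% | feasible |
| 16 | 100% | 80% | feasible |
| 15 | 100% | 75% | review and revise |
| 14 | 100% | 70% | review and revise |
| 12 | 100% | 60% | below 70% |
| 10 | 100% | 50% | below 70% |

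R does not move. The verdict under P first differs at 15 returned, that is, when 5 of 20 (25%) give nothing.

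**Case 2: only as many usable returns as the written rule needs to pass** (U is the smallest whole number with U / C at least 80%).

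| Return data | Usable | R = U/C | P = U/20 | Band under P |
|---|---|---|---|---|
| 18 | 15 | 83% | 75% | review and revise |
| 16 | 13 | 81% | 65% | below 70% |
| 15 | 12 | 80% | 60% | below 70% |
| 12 | 10 | 83% | 50% | below 70% |
| 10 | 8 | 80% | 40% | below 70% |

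Here the verdict already differs when 2 of 20 give nothing.

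**Should the two time points be pooled?** Suppose 12 of 20 are usable at baseline (12/20 = 60%, lowest band) and 20 of 20 after the intervention. Pooled, (12 + 20) / (20 + 20) = 32/40 = 80%, a pass. Pooling could hide a failed baseline, so the time points need separate percentages.

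**The case against.** The best case for the plan has four parts.

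- *The committees will see the gap.* The decision is described as informed by the baseline experience, section 4.1.2(b) brings in evidence from parallel studies, and the outputs are reviewed before any recommendation. Eight absentees among about 20 would be hard to overlook. This lowers the risk in practice. But the top band is firmly worded, and for this question the plan writes in committee consideration only below 70%, a band that absent data alone cannot trigger.
- *Large non-return at baseline may be unlikely.* Participants need internet access, a device and, where necessary, support. This bears on how often the rule would mislead, not on what it measures. It is also why the completion levels above are a range and not a forecast. With fully usable returns and 16 or more of 20 responding, both denominators give the same verdict.
- *The sponsor may have meant planned data.* If so, the repair is a clarification of wording.
- *The stakes are modest.* This is a secondary outcome of a small pilot without a comparison arm, and no effect estimate depends on it. That stands and limits the severity.

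A reader might also infer two stronger points that the documents do not support. One is that non-completion of any kind is invisible. A part-completed measure has been collected and could be judged unusable, which would lower the score. The plan does not say either way, so the point is secure only where there are no data at all. The other is that eligibility pre-selects people who will pass, because participants must be "albe to complete the outcome measures (with or without support) and engage with the STORM intervention". That criterion does not mention remote completion and it allows support. Who is screened out is a separate question of generalisability.

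**Conclusion.** The concern holds for participants and measures that yield no data: followed exactly, the rule can declare remote collection feasible when the usable share of expected data is below the plan's own cut-offs. With 20 participants and fully usable returns, the verdict is wrong once 5 or more return nothing. With imperfect returns it can be wrong sooner: 13 usable out of 16 returned reads 81% as written but is 65% of 20.

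These figures rest on assumed completion levels and on one data unit per participant. That the written score cannot be lower than the expected-data score depends on neither assumption. The documents do not show that non-return will be high, or that the committees would ignore it. The change should be made before the month 8 review. The defect does not undermine the pilot as a whole.

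**What to change.** In section 4.1.4, change the denominator in all three bands from collected outcome data to expected baseline outcome data. Define expected as every consented pilot participant multiplied by every planned baseline measure. Define usable for each measure, and state that a measure not obtained or not scorable counts as not usable. The existing sentence tying the decision to baseline can then stay.

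Report the same percentage separately for the post-intervention measures in section 4.1.3, without combining it with baseline.

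The cost is a few words and a tally of measures due against measures obtained. The downside for the sponsor is that, for a given unit and definition of usable, the baseline percentage can only stay the same or fall.
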